6.4.2.8 Entry to Maintenance Phase

Following completion of Week 24 of the Induction Phase, subjects will be eligible for entry into the Maintenance Phase if none of the conditions listed below are met, and based on Investigator clinical judgement, it is in the best interest of the subject to continue study participation. Subjects who do not qualify for entry to the Maintenance Phase will be eligible for participation in the OLE Study, CC-93538-EE-002, unless permanent discontinuation from IP has occurred. The following are conditions that will exclude subjects from entry to the Maintenance Phase:

- Subjects with a severe EoE flare as described in Section [6.4.2.7](#)
- Subjects who demonstrate a significant worsening upon endoscopic assessment at Week 24 compared to baseline as evidenced by the development of severe rings (ERES Grade 3), a stricture < 10 mm, or a stricture that requires dilation, as evaluated by the Investigator; any other significant findings that, in the opinion of the Investigator, could potentially disqualify a subject from entering the Maintenance Phase must be assessed in conjunction with the Medical Monitor to determine if the subject is eligible for participation in the OLE Study, CC-93538-EE-002
- Subjects who are permanently discontinued from IP during the Induction Phase (before or at Week 24), and these subjects will not be eligible for participation in the OLE Study, CC-93538-EE-002 (see Section [11.1](#))
- In addition, for subjects who meet the following condition during the first 24 weeks of treatment (and without a severe EoE flare), a discussion with the Medical Monitor will be required before entry into Maintenance:
 - Subjects with any protocol-prohibited use of or change to diet (eg, food elimination) or medication which will impact efficacy assessment for CC-93538 (as determined through consultation with the Medical Monitor) will be excluded from entry to the Maintenance Phase

By contrast, subjects requiring concomitant systemic corticosteroids for an indication other than EoE may be eligible for entry to the Maintenance Phase if the duration of therapy is no more than 10 days and use does not occur within the 6 weeks preceding Induction Phase Week 24.

Note that subjects with use of systemic immunosuppressive or immunomodulating drugs prohibited per protocol (see Section [8.2](#)) will be permanently discontinued from IP and will not be eligible for the OLE study (refer to Section [11.1](#)).

For any subject in which there are no disqualifying criteria but the Investigator does not believe it is in the best interest of the subject to continue on into the Maintenance Phase, a discussion with the Medical Monitor will be required prior to decision to transition to the OLE study.

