3 OVERALL STUDY DESIGN

3.1 Study Design

The Phase 3 program includes a multicenter, multinational, randomized, double-blind, placebo-controlled induction and maintenance study to evaluate the efficacy and safety of CC-93538 in adult and adolescent subjects with EoE (Study CC-93538-EE-001) with a separate, optional Open-Label Extension Study (OLE; Study CC-93538-EE-002). Globally, the study includes both subjects who have had an inadequate response to or are intolerant to corticosteroid therapy (Steroid Inadequate Responders/Intolerant; approximately 70% of the study population) as well as subjects who are naïve or have had an adequate response to corticosteroid therapy (Steroid Responders/Naïve; approximately 30% of the study population). However, in Germany, Spain, and the United Kingdom, only subjects who have had an inadequate response to corticosteroid therapy or are intolerant to corticosteroid therapy will be enrolled in the studies. Also, in Austria, Germany, Spain, and Switzerland, adolescent subjects will not be enrolled. The study will include a 24-week Induction Phase followed by a 24-week Maintenance Phase. Subjects will be randomized at the beginning of the study into 3 treatment arms: placebo for Induction and Maintenance, CC-93538 360 mg SC once weekly for Induction followed by 360 mg SC once every other week for Maintenance, or CC-93538 360 mg SC once weekly for Induction and Maintenance. All subjects will receive CC-93538 360 mg SC once weekly in the optional OLE

study; the dosing regimen may be revised through an amendment to the OLE study protocol once results from Study CC-93538-EE-001 are available and the most effective and safest dosing regimen is confirmed. An overview of the study design is presented in [Figure 1](#).

Figure 1: Overall Study Schema

Abbreviations: EGD = esophagogastroduodenoscopy; EoE = eosinophilic esophagitis; IP = investigational product; N = sample size; OLE = Open-Label Extension; SC = subcutaneous injection

This study will empanel a steering committee (Section [9.9.5](#)), and safety monitoring will be performed by an external, independent Data Monitoring Committee (Section [9.9.4](#)) in addition to routine internal review by the Safety Management Team (Section [9.9.3](#)).

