- A severe EoE flare is defined as any worsening of EoE symptoms including a high intensity episode resulting in emergency department visit or hospitalization, with the need for endoscopic intervention (eg, for prolonged food impaction) and/or need for rescue therapy (eg, including but not limited to corticosteroid therapy or dilation), or a worsening of EoE symptoms resulting in the need for rescue therapy only without endoscopic intervention.
- A mild to moderate EoE flare is defined as any worsening of EoE symptoms without the need for rescue therapy or endoscopic intervention.

ET procedures performed at the EoE Flare Assessment Visit do not need to be repeated for subjects who discontinue the study prematurely due to an EoE flare.

Induction Phase

In the Induction Phase, if a subject experiences a severe EoE flare requiring intervention with endoscopy and/or treatment with any rescue therapy (eg, including but not limited to systemic or swallowed topical corticosteroid therapy or dilation), the subject may continue participation in the Induction Phase with concomitant rescue therapy as needed until completion of the Induction Phase at Week 24. The subject will not meet the entry criteria for the Maintenance Phase. The subject will be eligible to enroll in the OLE Study, CC-93538-EE-002, based on the judgement of the Investigator after completing Week 24 of the Induction Phase.

Subjects participating in the Induction Phase who require pharmacotherapy or dietary modifications prohibited by the protocol that may affect CC-93538 efficacy assessment or a dilation procedure will not be eligible for entry into the Maintenance Phase. Refer to Maintenance entry criteria in Section [6.4.2.8](#).

Maintenance Phase

In the Maintenance Phase, if a subject experiences a severe EoE flare requiring intervention with endoscopy and/or treatment with any rescue therapy (eg, including but not limited to systemic or swallowed topical corticosteroid therapy or dilation), the subject may continue participation in the Maintenance Phase with concomitant rescue therapy as needed until completion of the Maintenance Phase at Week 48. The subject will be eligible to enroll in the OLE Study, CC-93538-EE-002, based on the judgement of the Investigator after completing the study (Week 48).

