9.3 Sample Size and Power Considerations

A total sample size of 399 subjects (266 subjects for CC-93538 and 133 subjects for placebo) with a 20% dropout rate at the end of the Induction Phase (212 subjects for CC-93538 and 106 subjects for placebo) will provide at least 90% power to detect a difference of -2.79 change in DD from

baseline at Week 24 and at least 90% power to detect a difference of 15% at Week 24 in histologic response with a two-sided significance level (alpha) of 0.05. These calculations were based on a 2 sample t-test assuming a pooled standard deviation of 4.76 for change in DD from baseline and the chi-square test to compare the difference in 2 independent proportions for the histologic response assuming that the true placebo response proportion is 0.05.

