9.6.3 Analysis of Secondary Efficacy Endpoints

End of Maintenance Phase (Week 48):

Histologic Response: The analysis of the histologic response endpoint will be conducted on the ITT population using the CMH test stratified by Steroid Inadequate Responders/Intolerant status. For treatment comparison between a CC-93538 dose and placebo, the 2-sided 95% CI for the difference in proportions using the CMH weights will be provided. Missing data will be handled via the same strategy as for the primary analysis of the co-primary endpoint of histologic response.

Mean change in DD: For the analysis of change in DD from baseline at Week 48, the baseline is defined as the last visit prior to receiving any dose of CC-93538 360 mg or placebo in the Induction Phase. The analysis of change in DD from baseline at Week 48 will be conducted using an ANCOVA model with treatment group (CC-93538 360 mg SC once weekly, CC-93538 360 mg SC once every other week, and placebo), Steroid Inadequate Responders/Intolerant status (yes or no), and baseline DD values included in the model. Point estimates for the mean difference between the treatment groups using the adjusted LS Mean changes and corresponding 95% Wald

CI will be reported. Missing data will be handled via the same strategy as for the primary analysis of the co-primary endpoint of change in DD.

[figure not shown]
In addition to the overall population, histologic response at Week 48 and change in DD from baseline to Week 48 will be analyzed in the Steroid Inadequate Responders/Intolerant subgroup. These analyses will be similar to the overall population except that the analysis will be done using the chi-square test and the ANCOVA model will not include Steroid Inadequate Responders/Intolerant status. See Section 9.6.4 for details on the hierarchical testing procedure to control the Type I error rate.

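### Subjects kept out of Maintenance at Week 24 for endoscopic worsening without dilation, or moved to the OLE on Investigator judgement, fall under no listed intercurrent event, so their Week 48 outcomes are imputed as if they had continued blinded treatment

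*Combined protocol and SAP*

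**What the plan says.** **Leaving at Week 24.** Section 6.4.2.8 lists conditions that bar entry to Maintenance. One is "Subjects who demonstrate a significant worsening upon endoscopic assessment at Week 24 compared to baseline", shown by new severe rings, a narrow stricture, or a stricture needing dilation. Another is a severe flare. Subjects who do not qualify may join the OLE unless permanently off investigational product. Where nothing disqualifies the subject but the Investigator thinks continuing is not in the subject's interest, "a discussion with the Medical Monitor will be required prior to decision to transition to the OLE study". Section 3.1 adds: "All subjects will receive CC-93538 360 mg SC once weekly in the optional OLE" study. Under Section 6.2.2, OLE entrants finish this study at the Week 24/ET Visit.

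**Intercurrent events.** The Protocol Summary and Tables 7 and 8 define two. ICE 1 is stopping treatment without rescue or prohibited medication; the Summary confines it to people who stay in the study, and it is handled by treatment policy. ICE 2 is rescue or prohibited medication, handled as composite failure. The tables limit both to the period ahead of Week 24.

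**Week 48 analysis.** Section 9.6.3 analyses histologic response in the ITT population, and Section 9.2 makes ITT primary for all efficacy parameters. For histology, "Missing data will be handled via the same strategy as for the primary analysis of the co-primary endpoint of histologic response"; the text for dysphagia days (DD) is parallel. Section 9.6.2, on the Week 24 key secondary endpoints, carries over both the missing-data and the intercurrent-event handling. Section 9.6.4 places two Week 48 endpoints in the fixed sequence, overall and in the steroid subgroup; Section 9.6.3 identifies these as DD and histologic response.

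**The concern.** Some of these subjects leave because the protocol itself classes their Week 24 findings as a significant worsening. The plan treats rescue use as treatment failure, yet someone removed for new severe rings receives a modelled on-treatment value at Week 48. That is a hypothetical strategy applied by default, and it sits badly with the logic behind ICE 2.

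Persistence of effect, including on every-other-week dosing, is a stated objective. A subject assigned to that arm who leaves at Week 24 has received only weekly dosing, yet would be imputed from subjects who actually took the less frequent regimen.

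The flare and rescue endpoints also run through Week 48. A subject excluded on endoscopic findings may leave at Week 24 with no event recorded. The protocol does not say how that follow-up is censored.

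**Working it through.** **1. The plan's own figures.** Section 9.3 gives "A total sample size of 399 subjects (266 subjects for CC-93538 and 133 subjects for placebo") and a "20% dropout rate at the end of the Induction Phase (212 subjects for CC-93538 and 106 subjects for placebo"), "with a two-sided significance level (alpha) of 0.05". It assumes a DD difference of -2.79 with SD 4.76, and histologic response of 5% on placebo with a 15-point difference.

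- Evaluable numbers: 0.8 x 266 = 212.8 and 0.8 x 133 = 106.4, matching 212 and 106.
- DD: SE = 4.76 x sqrt(1/106 + 1/212) = 0.566; 2.79/0.566 = 4.93; power = Phi(4.93 - 1.96) = 99.8%.
- Histology, 20% versus 5%: power 97.3% (95.7% with continuity correction).

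Both meet the stated 90%. The protocol gives no power for Week 48 and no expected number of Week 24 transfers.

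**2. Which rule reaches each subject?**

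| Situation at Week 24 | ICE 1 | ICE 2 | Week 48 data here |
|---|---|---|---|
| Endoscopic worsening, no dilation | No | No | None |
| Investigator judgement, OLE | No | No | None |
| Stricture dilated before Week 24 | No | Yes | None |
| Severe flare with rescue | No | Yes | None |
| Severe flare, endoscopy only | No | Wording conflicts | None |

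The first two rows assume no other rescue or prohibited medication. ICE 1 does not apply because OLE entrants do not stay in the study and by rule are not permanently off product. Treatment policy would in any case have no Week 48 observation to use. ICE 2 does not apply because Section 7.2.6 describes rescue as standard-of-care drugs, diet or dilation, and Section 8.2 exempts the study product from its ban on anti-IL-13 antibodies.

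**3. Who informs the imputation?** Subjects who stop product during Induction also leave the study (Section 11.1). Observed Week 48 values therefore come only from Maintenance entrants. Subjects with newly developed severe rings are excluded by rule, so no comparable subject has an observed value and the model must extrapolate. Tipping-point analysis is described only for the Week 24 co-primary endpoints.

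**4. Size for histology.** Let sA and sP be the transfer shares, and pA and pP the Week 48 response rates. Assumptions: the design rates (20%, 5%) hold at Week 48, and transfers are imputed at their arm's mean.

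- Difference under imputation: pA - pP = 15.0 points.
- Difference under composite handling: pA(1 - sA) - pP(1 - sP).
- Overstatement: sA x pA - sP x pP, which is s x (pA - pP) when the shares are equal.

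| sA, sP (assumed) | Composite difference | Overstatement | Power, 133 v 133 |
|---|---|---|---|
| 0, 0 | 15.0 | 0 | 0.963 |
| 5%, 5% | 14.25 | 0.75 | 0.953 |
| 10%, 10% | 13.5 | 1.5 | 0.941 |
| 10%, 5% | 13.25 | 1.75 | 0.930 |
| 5%, 20% | 15.0 | 0 | 0.973 |
| 2%, 10% | 15.1 | -0.1 | 0.970 |

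The sign turns when sP/sA exceeds pA/pP = 20/5 = 4. Power treats imputed values as observed, so it is on the high side. If active response were 50% (assumption), the equal-share overstatement would be 0.05 x 45 = 2.25 and 0.10 x 45 = 4.5 points.

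Whatever the balance, each arm's own rate exceeds its composite value by up to s x p. At 5% transfer that is 1.0 point on active and 0.25 on placebo; at 10%, 2.0 and 0.5.

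**5. Size for DD.** With placebo mean change m and worst change w, the composite difference is -2.79(1 - sA) + (sA - sP)(w - m). Equal shares give -2.65 at 5% and -2.51 at 10%. For m from -3 to -5 and w from 0 to +10 (assumed), 2% active with 10% placebo gives -2.97 to -3.93, and 10% active with 5% placebo gives -2.36 to -1.76.

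**The case against.** **SAP deferral.** Section 9.1 leaves unexplained details to the SAP. The SAP text was not in the copy reviewed, which also has a gap in Section 9.6.3. A Week 48 estimand may exist there. This stands as a caveat, but the protocol does state a Week 48 rule, and that rule covers missing data only.

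**Imputation need not be generous.** The design is treat-through and Maintenance entry requires no response, so Week 24 non-responders are among those who inform the model. The Week 24/ET Visit includes EGD and diary, so poor Week 24 values are available to it. A reader might infer that transfers are credited with the outcomes of subjects who did well. The documents do not support that. The imputation model is not given, and conditioning on Week 24 would soften the bias without making the strategy a deliberate choice.

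**Direction.** A reader might infer that the plan inflates the treatment effect. That holds for equal transfer but not in general, as the table shows.

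**Routes.** A reader might infer guaranteed active drug. The OLE is optional, and the judgement route needs a Medical Monitor discussion. A reader might also count a severe flare managed by endoscopy alone as a settled third route. Section 6.4.2.7 defines a severe flare "with the need for endoscopic intervention (eg, for prolonged food impaction) and/or need for rescue therapy", but the same section, with 7.2.6 and 8.1.1, also ties severe flare to needing rescue, and the rescue list is open-ended. That is a wording conflict, not an established gap.

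**Composite for every judgement transfer.** Best interest need not mean lack of efficacy. Forcing a Week 24 responder to failure could make a confirmatory outcome depend on discretion. This objection is accepted and shapes the fix.

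**Conclusion.** The point stands for two groups: endoscopic worsening without dilation, and transfer on Investigator judgement. Neither is an intercurrent event in the visible text, neither has Week 48 data in this study, and the stated rule gives both a hypothetical on-treatment outcome in confirmatory Week 48 analyses. The underlying gap is wider, because Section 9.6.3 states no intercurrent-event handling for Week 48 at all.

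The effect is probably modest at the design rates: 0.75 to 1.5 points on the histology difference for 5% to 10% equal transfer, as an upper illustration. Its true size and sign cannot be found from the documents, because transfer rates, their balance between arms and the imputation model are not given. The Week 24 co-primary endpoints are unaffected by these departures, which follow the Week 24 assessments. The change is worth making before database lock; if the SAP already holds a Week 48 rule for these subjects, the point reduces to a cross-reference.

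**What to change.** 1. In Section 9.6.3 and the SAP, state that intercurrent-event handling applies to the Week 48 endpoints, with the window extended to Week 48.
2. Add a Week 48 intercurrent event: non-entry to Maintenance, or transition to the OLE, because of endoscopic worsening or severe flare. Handle it by the composite strategy already used for ICE 2 (histologic non-responder; worst value for change in DD).
3. For Investigator-judgement transfers, record the reason at the time of the decision. Apply the composite when the reason is lack of efficacy or worsening; otherwise keep multiple imputation. Add a sensitivity analysis counting all such transfers as failures.
4. Add a sensitivity analysis of time to flare and time to rescue through Week 48 that counts a failure-driven transfer as an event.
5. Reconcile Sections 6.4.2.7, 7.2.6 and 8.1.1 on whether a severe flare managed by endoscopy alone counts as rescue, so that its ICE 2 status is clear. Which reading applies is for the sponsor.

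Cost: protocol or SAP wording and one eCRF reason field, since the discontinuation reasons in Section 11.2 do not separate these routes. No extra visits or subjects are needed. Week 48 response rates may become slightly less favourable; under the assumptions above, Week 48 histology power stays at 0.93 or higher.

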6.5 Anti-drug Antibody Assessments

Serum samples to assess blood levels of antibodies to CC-93538 will be obtained pre-dose (except for the ET Visit and 2 Safety Follow-up Visits, if applicable) at the time points outlined in the Table of Events ([Table 4](#) and [Table 5](#)).

Details of the procedures to be followed for sample collection, processing, storage, shipment, and testing will be documented in a separate Study Laboratory Manual.

The development of anti-CC-93538 antibodies will be monitored to assess the impact of immunogenicity on safety, PK, and efficacy of CC-93538. The impact of immunogenicity will be evaluated by considering the results of PK, [REDACTED] and immunogenicity data taken together. Samples will be stored for additional analysis if necessary.

[figure not shown]
Further analysis on samples that are positive for ADA may be performed, including assessment of neutralizing antibodies when warranted. Samples will be stored for up to 5 years after study completion.

[figure not shown]
6.6 Pharmacokinetics

[figure not shown]
6.6.1 Serum CC-93538 Assessments

Serum samples to assess CC-93538 concentrations will be obtained pre-dose (except for the ET Visit and 2 Safety Follow-up Visits, if applicable) at the time points described in the Table of Events ([Table 4](#) and [Table 5](#)). In the event that dosing occurs during a non-clinic visit day, it is still acceptable to obtain the serum samples.

Details of the procedures to be followed for sample collection, processing, storage, shipment, and testing will be documented in a separate Study Laboratory Manual.

7 DESCRIPTION OF STUDY TREATMENTS

7.1 Description of Investigational Product(s)

The active ingredient of CC-93538 is a recombinant humanized IgG1 monoclonal antibody directed against human IL-13. Investigational products (CC-93538 and placebo solutions for injection) are to be stored at 2° to 8°C. The IP should not be frozen. The labeling will be in accordance with GCP and any other local regulatory requirements. During the study, IP will be dispensed in pre-filled syringes (PFS) provided by the Sponsor.

The 360 mg dose of CC-93538 (or placebo) will be administered by 2 injections of 1.2 mL each at a concentration of 150 mg/mL CC-93538.

Specific handling and dispensing instructions associated with each presentation of IP are provided below.

IP in PFS

A PFS presentation containing drug product at a concentration of 150 mg/mL CC-93538 (or placebo) in a 1.2 mL fill will be utilized in the study. CC-93538 solution for injection (or placebo) will be provided as a sterile liquid in PFS at a concentration of 150 mg/mL (or placebo) packaged in cartons (2 PFS per carton). CC-93538 and placebo solutions differ slightly in physical appearance and when presented in vials, the slight color difference in IP cannot be fully blinded. Therefore, for the PFS a label cover on the active and placebo syringes (to be applied during packaging/labeling) will be used to maintain the blind. As the PFS packaging will sufficiently blind the syringe contents, an unblinded pharmacist will not be required to dispense IP in the PFS. At home self-administration (as outlined in Section 7.2.1) or administration of IP through a home health nurse (as outlined in Section 7.2) will be available IP administration options with the PFS.

Additional instructions related to IP handling, preparation, and dispensation will be provided in a separate Study Pharmacy Manual (including an Instructions for Use document).

